10.1 Power Calculations

The primary endpoint is final infarct size (% of left ventricle mass) measured by LGE on CMR at 3 months. Based on results of the CMR sub-studies of the DANAMI-3 trial⁴⁰⁻⁴⁵, the mean final infarct size measured by LGE on CMR is 13% with a standard deviation (SD) of 9% in patients with STEMI. To demonstrate a relative reduction in final infarct size of 20% with a two-sided alpha level of 0.05 and a power of 80%, recruitment of 378 patients is needed. A drop-out rate of 40% is expected for the primary endpoint. Therefore, we expect to randomize 530 patients in total. However, patients will be included until 378 patients have completed the CMR at 3 months. The power calculations have been calculated by a biostatistics professor.

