6.2 Target Patient Population and Number of Patients

The target patient population is male and female patients aged 18 years and over with documented evidence of STEMI, eligible planned for primary PCI who had symptom onset within 12 hours before randomization who were initially managed by an ambulance paramedic and included by the referring and including doctor (on-call cardiology fellow doctor (RD) at Rigshospitalet) in the *pre-hospital* setting.

A total of 378 patients with STEMI (189 patients treated with intravenous infusion of 250 mg methylprednisolone and 189 patients with intravenous placebo infusion) are included for the primary endpoint of final infarct size (% LGE of the LV) on CMR at 3 months. The inclusion will continue until this number has been reached and with an expected drop-out rate of 40%, 530 patients need to be included and randomized. All patients will be included in the *pre-hospital* setting from throughout the Capital Region and Region Zealand of Denmark (Figure 2).

Figure 2. Flowchart of the study

[figure not shown]

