6.4 Estimated Study Duration

We expect the study to begin once the study has been approved by the government. Rigshospitalet performs approximately 1000 primary PCI procedures per year³⁴. An inclusion is planned to be completed in 36 months, and the 3-months follow-up period will be completed after 39 months. However, the study will be stopped before when 378 patients have completed CMR at 3 months. Following completion of the trial, the hospital records will be accessed at 1 and 10 years to obtain information on mortality and hospitalization for HF (Figure 3).

Figure 3. Timeline of the study

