### Sample Size

The sample size was calculated based on the primary outcome of final infarct size measured by late gadolinium enhancement (LGE) on cardiac magnetic resonance (CMR) at three months. Based on results of the CMR sub-studies of the DANAMI-3 trial, the mean final infarct size measured by LGE on CMR is 13% with a standard deviation (SD) of 9% in patients with ST-segment elevation myocardial infarction (STEMI). The trial was powered to demonstrate a reduction in final infarct size of 20% with a two-sided alpha level of 0.05 and a power of 80% requiring 378 patients. A drop-out rate of 30% was expected for the primary outcome but will be adjusted according to the actual drop-out rate. Inclusion of patients will continue until 378 has completed the follow-up CMR.

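### The stated randomised total of 530 does not follow from 378 completers and 40% drop-out, which need 630, and the SAP gives a different drop-out rate

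*Protocol*

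**What the plan says.** Protocol section 10.1 bases the sample size on final infarct size: "the mean final infarct size measured by LGE on CMR is 13% with a standard deviation (SD) of 9% in patients with STEMI". For a 20% relative reduction, "with a two-sided alpha level of 0.05 and a power of 80%, recruitment of 378 patients is needed". It then inflates for loss: "A drop-out rate of 40% is expected for the primary endpoint. Therefore, we expect to randomize 530 patients in total". Section 6.2 repeats the inflated figure as a requirement: "with an expected drop-out rate of 40%, 530 patients need to be included and randomized".

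The SAP, under Sample Size, keeps the 378 but gives another rate: "A drop-out rate of 30% was expected for the primary outcome but will be adjusted according to the actual drop-out rate". It states no randomised total.

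Both documents also fix when recruitment ends. Protocol sections 6.2, 6.4 and 10.1 and the SAP's Sample Size section all continue inclusion, or run the study, until 378 patients have had the three-month CMR. Section 6.4 adds a planned duration: "An inclusion is planned to be completed in 36 months".

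**The concern.** A drop-out rate is normally a share of the patients randomised, so the required number of completers is divided by one minus the rate. The protocol's 530 does not satisfy that relation at its own 40%. The SAP's 30% does not explain the figure either, and neither document says which rate is the planning value.

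What is at stake is the stated size of the trial. Study medicine is given in the ambulance and consent is sought after primary PCI (Protocol sections 7, 9.1 and 9.2.1). The expected number randomised is therefore the number of people expected to be exposed before they can agree. It appears twice in the protocol that goes to the ethics committee, and it is the natural basis for planning study-medicine supply, scanner time and duration.

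**Working it through.** **Inputs**
- Control mean 13% of LV mass, SD 9%, 20% relative reduction, two-sided alpha 0.05, power 80% (Protocol 10.1).
- 1:1 allocation, 189 per arm (Protocol 6.2 and 8.3).
- Drop-out 40% (Protocol 6.2 and 10.1) or 30% (SAP, Sample Size).
- Randomised total 530 (Protocol 6.2 and 10.1).
- Inclusion period 36 months (Protocol 6.4).

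**Step 1: reproduce the completer target.** The difference is Δ = 0.20 × 13 = 2.6 percentage points.

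n per arm = 2(1.960 + 0.842)² × 9² / 2.6² = 188.1, rounded up to 189, so 378 in total. The t-based calculation gives 189.06 per arm. The 378 is correct.

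**Step 2: inflate for drop-out.** With d the share of randomised patients without a three-month scan, N = 378/(1 − d).
- d = 0.40: 378/0.60 = 630.
- d = 0.30: 378/0.70 = 540.

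The protocol's 530 is 100 below the first figure (100/530 = 19%) and 10 below the second.

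**Step 3: where 530 may come from.** 378 × 1.4 = 529.2, which rounds up to 530. The protocol shows no formula, so this is an inference from the numbers. Working backwards, 1 − 378/530 = 28.7%, so 530 fits a drop-out rate that neither document states.

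**Step 4: completers from 530, if recruitment were to end there.** Power ≈ Φ(Δ / (σ√(2/n)) − 1.960), with n per arm.

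| Completers | How obtained | Power, normal | Power, t-based |
|---|---|---|---|
| 378 | documented recruitment rule | 80.2% | 80.0% |
| 371 | 530 × 0.70 | 79.5% | 79.2% |
| 318 | 530 × 0.60 | 73.1% | 72.8% |

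For 318 completers: n = 159 per arm, 9 × √(2/159) = 1.009, 2.6/1.009 = 2.576, and Φ(2.576 − 1.960) = 0.731.

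**Step 5: recruitment pace needed for the 36 months.** 530/36 = 14.7 patients per month; 630/36 = 17.5 per month. The documents give no expected recruitment rate to compare with these, only about 1000 primary PCI procedures per year at the centre (Protocol 6.4).

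**The case against.** The strongest answer is that recruitment is governed by completers and not by 530. Section 10.1 calls 530 an expectation, and its next sentence continues inclusion until 378 scans are done. Section 6.2 does say that 530 need to be randomised, but in the same sentence as the completer rule. The SAP restates that rule and says the drop-out rate will be adjusted to what is observed. All of this stands. A reader might infer from the 318 completers that the trial is underpowered by design, at about 73%. The documents do not support that: nothing caps enrolment at 530, and under the written rule power stays at 80%.

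A reader might also infer a late finish or a budget shortfall. At 14.7 per month, 630 patients would take 630/14.7 ≈ 43 months. But that pace assumes the 36 months was derived from 530, which the protocol does not say; at 17.5 per month 630 fits within 36 months. The preliminary budget in section 14 is not tied to any patient number. Neither consequence can be asserted.

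One could argue that 40% was meant as an addition to 378. The extra 152 patients are indeed 40.2% of 378. But they are 28.7% of those randomised, and a reader told to expect 40% drop-out would not understand it that way.

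Finally, the SAP never uses 530, and at its 30% the gap is only 10 patients and less than one point of power. That is fair: the material discrepancy lies inside the protocol. Still, two documents that each report a different expected rate for the same endpoint need to be reconciled.

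**Conclusion.** Wrong as written, as an error in the planned enrolment figure. With 378 completers and 40% drop-out, the expected randomised total is 630 and not 530: 100 more patients, or 19%, would be randomised and treated before consent if the protocol's own rate occurs. At the SAP's 30% the total is 540. The documents disagree on the rate, and 530 matches neither.

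The completer target, the effect size and the 80% power are unaffected as long as the recruit-to-378 rule is carried through. The figure of about 73% applies only if recruitment ended at 530 with 40% drop-out; at 30% it would be about 79%.

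The conclusion assumes that drop-out means the share of randomised patients without the three-month CMR. That the 530 came from multiplying by 1.4 is likely, but the conclusion does not depend on it.

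**What to change.** - In Protocol sections 6.2 and 10.1, restate the expected randomised total as 630 if 40% is kept, or 540 if 30% is adopted, and show the calculation as 378/(1 − drop-out rate).
- Use one expected rate in the protocol and the SAP, and say that it is a share of those randomised. If the rate was revised between the documents, say so and give the reason.
- Check the 36-month inclusion period in section 6.4 against the corrected total. It implies an average of 17.5 patients per month at 630, or 540/36 = 15 per month at 540.
- Keep the rule of recruiting until 378 patients have completed the scan.

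The cost is a change of wording in two or three protocol sections and one in the SAP, and a larger, less favourable stated enrolment. The design, the analysis and the completer target do not change.

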10.2 Statistical Analysis

For patients fulfilling all in- and exclusion criteria, the treatment groups will be compared as intention-to-treat principle. Additional as-treated analyses will be performed. Patients included that subsequently are excluded due to meeting exclusion criteria will be considered screen failure. These patients will still be followed for safety reasons. Differences between group means/medians will be assessed with parametric or non-parametric statistics accordingly. Chi-square analysis or Fisher's exact test will be used to test differences between categorical variables. Differences between groups in the time-to event secondary endpoints will be assessed using Kaplan-Meier and Cox regression model. In case of an event or until last patient has been followed, the patients will be censored. Probability of survival will be displayed using Kaplan-Meier methodology. Hazard ratios between groups will be calculated using a Cox proportional hazard model. A two-tailed P-value <0.05 is considered statistically significant.

10.3 Pre-specified Subgroup Analyses

The primary endpoint will be compared between treatment groups in pre-specified subgroup analyses: age, gender, pre-PCI TIMI flow, culprit in LAD, time from first medical contact to primary PCI, and duration from symptom to primary PCI. These subgroups will be analyzed using interaction tests. The pre-specified subgroups are factors that are known to influence the clinical course in patients with STEMI.

11. Sub-study

Prior studies have shown that reperfusion injury following primary PCI in patients with STEMI is equivalent to damage in the microcirculation causing microvascular dysfunction. The microvascular function can be investigated by thermodilution-derived parameters including CFR and IMR as well as absolute flow and absolute resistance. Prior studies in STEMI patients have shown that IMR has a prognostic value and correlates to MVO. Glucocorticoid may limit reperfusion injury by decreasing the inflammatory response in direct proximity to the microcirculation. To investigate this hypothesis, we will measure CFR and IMR on eligible patients included in PULSE-MI directly after initial primary PCI but before the catheter is removed.

CFR and IMR is measured by a pressure gauge wire and a 2-minute infusion of adenosine. This procedure will only prolong the normal PCI by 5 minutes and does not add any additional risk to the procedure and does not increase the risk of complications. The patient may experience a brief

feeling of shortness of breath during the infusion of adenosine but is not associated with other complications or side effects. Adenosine is often used in standard coronary angiography (CAG) and PCI procedure.

12. Data Storing and Handling of Personal Data

All study data will be stored pseudo-anonymously for 25 years. Data of the included patients with STEMI will be stored at an electronic database, RedCap, where data will be blinded, and patients will be identified by a study identification number only. Study participation will be annotated in the medical record of the patient.

13. Assessments of Safety and Harm

Mortality following STEMI has decreased after implementation of primary PCI and drug-eluting stents (DES), yet the 1-year mortality rate has unsatisfactorily plateaued at approximately 10%. Primary PCI is performed daily at Rigshospitalet, Copenhagen University Hospital, and the risks associated with the procedure is well known. STEMI is often complicated by a myocardial dysfunction leading to HF and arrhythmias during the acute phase. However, mechanical complications such as free wall rupture, ventricular septal rupture, and papillary muscle rupture may also occur in the setting of STEMI¹⁰. These complications are well known, and, as part of standard care, an echocardiography is performed in all patients admitted for primary PCI to assess potential mechanical complications and the function of the left and right ventricle. AEs/SAEs potentially related to the intervention of the study will include: death, infection, gastroduodenal ulcer, hypertension, fluid retention resulting in peripheral edema, anaphylaxis, and skin complications such as acne, atrophy, purpura, and wound healing complications. The half-life of methylprednisolone is 12 hours, and the drug is considered eliminated following 5 half-times. Therefore, AEs will be recorded for the first 3 days following intervention.

13.1 Adverse Events (AEs)

AEs are considered any untoward medical occurrence in the patient to whom intervention (methylprednisolone) has been administered and which does not necessarily have a causal relationship with this treatment. The AEs that will be recorded is infection and any skin complications.

13.2 Serious Adverse Events (SAEs)

The Principal Investigator and other Investigators will report all SAEs to Sponsor within 24 hours of awareness. All SAEs are any toward medical occurrence that at any dose requires inpatient hospitalization or prolongation of existing hospitalization, results in persistent or significant disability or incapacity, results in a congenital anomaly or birth defect, is life-threatening, or results in death.

All SAEs occurring from the time the study medicine has been administered until the patient has completed the trial will be reported by filling out and sending the SAE form within 24 hours, after the investigator becomes aware that the event meets the protocol definition of an SAE. Patients will therefore be followed for late-onset SAEs until completion of the trial (1 year).

Hospitalization and prolongation of hospitalization is defined as presentation at hospital for an urgent, unscheduled emergency department visit or hospital admission (>24 hours).

In the electronic database, REDCap, the following events will be reported: Death, hospitalization for heart failure, recurrent AMI, stroke/TIA, bleeding, and cardiac arrhythmia.

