Appendix B (End-point Definitions)

The clinical event committee (CEC) will review and adjudicate all occurrences of the clinical end-points according to the 2014 ACC/AHA Key Data Elements and Definitions for Cardiovascular Endpoint Events in Clinical Trials⁴⁶.

1. All-Cause Mortality
2. Recurrent Myocardial Infarction
3. Hospitalization for Heart Failure
4. Stroke/TIA

Mortality will to the extent possible be classified according to underlying disease. The CEC will classify the mortality as cardiovascular or non-cardiovascular death.

Cardiovascular mortality

Mortality considered as cardiovascular unless it is clearly attributable to another cause and thus includes:

- Death due to proximate cardiac cause (e.g. myocardial infarction, cardiac tamponade, worsening heart failure).
- Death caused by non-coronary vascular conditions such as neurological events, pulmonary embolism, ruptured aortic aneurysm, dissecting aneurysm, or other vascular disease.
- All procedure-related deaths, including those related to a complication of the procedure or treatment for a complication of the procedure.
- All valve-related deaths including structural or non-structural valve dysfunction or other valve-related adverse events.
- Sudden or unwitnessed death.
- Death of unknown cause.

Non-cardiovascular mortality

Any death in which the primary cause of death is clearly related to another condition (e.g. infection, cancer, suicide, accident, pulmonary, hepatobiliary, gastrointestinal, renal, overdose, neurological (excluding stroke and or cardiovascular hemorrhage of central nervous system)).

Hospitalization for heart failure is prolongation of hospitalization because of worsening of heart failure or presentation of the patient for an urgent, unscheduled clinic/office/emergency department visit or hospital admission (>24 hours), with a primary diagnosis of heart failure (HF), AND where the patient exhibits new or worsening symptoms of HF on presentation, AND has objective evidence of new or worsening HF*, AND receives initiation or intensification of treatment specifically for HF.

*Objective evidence consists of at least 2 physical examination findings OR at least 1 physical examination finding and at least 1 laboratory criterion (chest x-ray or BNP) of new or worsening HF on presentation.

Table 3. Value definition heart failure

Values	Value definition
New or worsening symptoms of HF	Dyspnea Decreased exercise tolerance Fatigue Volume overload

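### Section 13.2 defines prolongation of hospitalization as a presentation at hospital, so, read literally, an event that only lengthens the index stay is not a serious adverse event

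*Protocol*

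**What the plan says.** **The criterion (protocol, Section 13.2).** "All SAEs are any toward medical occurrence that at any dose requires inpatient hospitalization or prolongation of existing hospitalization". The other criteria are disability or incapacity, congenital anomaly, threat to life, and death.

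**The definition (same section, two paragraphs later).** "Hospitalization and prolongation of hospitalization is defined as presentation at hospital for an urgent, unscheduled emergency department visit or hospital admission (>24 hours". One definition serves both terms.

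**The trigger (same section).** The 24-hour report is due "after the investigator becomes aware that the event meets the protocol definition of an SAE".

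**Other capture.** Section 13 reasons from drug elimination, "The half-life of methylprednisolone is 12 hours, and the drug is considered eliminated following 5 half-times", to a recording window: "Therefore, AEs will be recorded for the first 3 days following intervention". Section 13.1 limits the content: "The AEs that will be recorded is infection and any skin complications". Section 13.2 adds a list of events for the electronic database: death, heart-failure hospitalization, recurrent infarction, stroke or TIA, bleeding and arrhythmia.

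**The comparison text (Appendix B).** For the heart-failure endpoint the two ideas are alternatives: "Hospitalization for heart failure is prolongation of hospitalization because of worsening of heart failure or presentation of the patient", followed by the types of visit that count.

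**The use (SAP, Statistical Analysis).** Adverse events, SAEs and serious adverse reactions are compared between arms in all randomized patients by Chi-Square or Fisher's exact test.

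**The concern.** A stay can be prolonged only in someone who is already an inpatient, and an inpatient does not come to the hospital again. The definition therefore does not fit one of the two terms it is meant to explain.

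Every participant is brought to hospital for the infarct shortly after the infusion. For a non-fatal early harm, lengthening of that stay is the natural way to become serious. If the definition is followed, such an event gets no SAE form and does not enter the SAE comparison. If the criterion is followed instead, it does both. Two investigators could classify the same event differently, and each could point to Section 13.2.

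**Working it through.** No sample-size or power figure enters this point. The check is a reading of the text plus one small calculation.

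**1. Does the definition leave room for prolongation?** There are two ways to parse it.
- Presentation governs both limbs: presentation for an emergency visit, or presentation for an admission of more than 24 hours. An event on the ward is neither.
- Presentation governs only the emergency visit, and an admission of more than 24 hours stands alone. The second limb still describes an admission. The index admission was caused by the infarct, and an event that extends it does not cause a new one.

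Neither parse describes an extension of stay. No other section gives a general definition of prolongation; Appendix B names it for heart failure only.

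**2. How much of the exposure falls in the index stay?** Section 13 gives a half-life of 12 h and elimination after 5 half-lives:

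5 × 12 h = 60 h = 2.5 days, which rounds up to the stated 3-day recording window.

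Section 8.8 has a blood sample taken on the ward after 24 hours. Section 8.9.3 has the acute scan done during admission within 48 hours, in patients without contraindications. The length of stay itself is not stated, so the shares below are for assumed stays, ignoring the short transport:

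| Index stay (assumed) | Share of the 60 h window |
|---|---|
| 24 h | 24/60 = 40% |
| 36 h | 36/60 = 60% |
| 48 h | 48/60 = 80% |
| 60 h or more | 100% |

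The mismatch in step 1 does not depend on these shares. They show only how much of the exposure it touches.

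**3. What other route catches such an event?** Take an event of a kind that Section 13 names as potentially related to the intervention. Suppose that it lengthens the index stay and is not fatal, life-threatening or disabling. With the definition read literally:

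| Event | Recorded as AE (13.1, 3 days) | Database list (13.2) | SAE |
|---|---|---|---|
| Infection | Yes | No | No |
| Skin complication | Yes | No | No |
| Ulcer with bleeding | No | Yes, as bleeding | No |
| Ulcer without bleeding | No | No | No |
| Hypertension | No | No | No |
| Fluid retention, not heart failure | No | No | No |

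The first three rows lose the serious label but remain on record. The last three may leave no record.

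**4. Does it reach the analysis?** Yes. The SAP tests SAEs as a category of their own, and what enters that category depends on the protocol definition.

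**The case against.** The strongest reply is that the criterion is clear and the later sentence is only badly worded. The criterion speaks of an existing stay, which can only mean a patient already admitted. The definition looks like a shortened copy of Appendix B in which the word separating the two alternatives was lost. A sensible investigator would report the event anyway. This stands in part: it rules out saying that no such event could ever be reported. It does not remove the problem, because reporting is tied to the protocol definition, and whether an event counts would depend on which sentence is followed.

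The second reply is that other routes capture much of the harm. This also stands. Infection and skin complications are recorded for 3 days, and Table 1 makes adverse events in the first seven days a safety endpoint. The SAP compares adverse events as well as SAEs. Bleeding and arrhythmia go into the database. What could be lost altogether is narrow, as the last three rows of the second table show.

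Four stronger inferences are tempting, and the documents do not support them.
- *All exposure falls in the index stay.* Its length is not given. A patient discharged before 60 h who returns would meet the definition.
- *The comparison between arms is biased towards no difference.* The same definition applies to both arms. Lost events mean lost information; a biased relative effect is not shown.
- *Expedited reports of unexpected reactions would be missed.* Section 13 itself anticipates infection and ulcer. Whether a reaction is unexpected depends on the product characteristics, which are not among the documents.
- *The 24-hour threshold is also an error.* A short unplanned admission through the emergency department already counts under the first limb, and Appendix B uses the same threshold.

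**Conclusion.** The point holds as an internal contradiction in Section 13.2 that affects safety reporting. Read literally, the definition excludes from the SAE category any non-fatal, non-life-threatening, non-disabling event that only lengthens the index stay. The probable consequence is inconsistent reporting and under-reporting of early SAEs in the SAP's comparison.

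Its size can be described but not counted. It affects one seriousness criterion, for a window of which an assumed stay of 36 to 60 h would cover 60% to 100%. The documents give no rate for such events, so any number of lost SAEs would be a guess. The conclusion assumes that at least some investigators apply the definition as written, and that patients spend much of the 60 h in hospital, as the ward sample and the in-hospital scan indicate. The primary endpoint, the sample size and the efficacy analyses are not affected.

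**What to change.** Reconcile the criterion and the definition in Section 13.2 by giving hospitalization and prolongation separate definitions. Use the structure of Appendix B, where prolongation and presentation are alternatives. Prolongation would then mean any untoward event that extends an existing stay, whether the index stay or a later one, with no new presentation needed. The definition of hospitalization, including its 24-hour threshold, can stay as it is, so that it continues to match Appendix B. Change the SAE form to the same wording.

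The cost is one sentence in the protocol, one edit to the form, and somewhat more SAE forms during the index stay. The SAP needs no change.
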